1. Calculate the 10 years incidence of total CVD, all-cause mortality and each major DM complication in Chinese DM patients in primary care.
2. Determine the risk factors that significantly predict total CVD, all-cause mortality and each major DM complication for Chinese DM patients in primary care.
3. Develop and validate risk prediction models for total CVD, all-cause mortality and each major DM complication for Chinese DM patients in primary care.
4. Develop a risk prediction nomogram and chart for the risk of total CVD, all-cause mortality for Chinese DM patients in primary care

Hypotheses

The following hypotheses will be tested:

1. Patient socio-demographic, clinical parameters, disease characteristics, and treatment modalities (these independent variables are described in the Methods section) are predictive of 10-year risk of total CVD, all-cause mortality and individual DM complication as a dependent variable.
2. The risk prediction models for total CVD, all-cause mortality and individual DM complication developed in this study can have over 70% of discriminating power.

d) **Plan of Investigation:**

(i) **Study design**

A 10-year retrospective study on a population-based cohort of Chinese DM patients in primary care.

(ii) **Subjects**

The cohort will include all patients with a documented clinical diagnosis of DM and were receiving care in the Hospital Authority (HA) primary care General Out-Patient Clinics (GOPC) and Family Medicine Clinics (FMC) on or before 1 July 2006 identified from the HA clinical management system (CMS) database.

Inclusion criteria

1. Age \geq 18 years old
2. At least 1 GOPC/FMC attendance on or within 1 year before 1 July 2006
3. Had a CMS record of the coding of ICPC-2 of T89 (Diabetes insulin dependent) or T90 (Diabetes non-insulin dependent) on or before 1 July 2006

Exclusion criteria

1. Patients who had a diagnosis of any DM complications defined by the relevant ICPC-2 or ICD-9-CM (shown in the Method section) on or before 1 July 2006.
2. Patients exclusively managed by Specialist Out-Patient Clinic (SOPC) on or before 1 July 2006.

Sample size calculation

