The detailed sample size calculation for each study outcome is attached in Appendix B. The required sample size is based on the requirements for the development and validation of the least common DM complication of ESRD. Specifically, based on our previous study, the 5-year incidence of ESRD was 1.9%(8), which can be extrapolated to a 10-year incidence of ESRD was 3.8% by assuming a constant incidence rate over time. To develop the risk prediction model for ESRD by multivariable Cox proportional hazard regressions with forward stepwise variables selection on 16 potential risks factors, we need 21,053 subjects using the 1 in 50 rule that 1 candidate predictor can be studied for every 50 events (23). To validate the risk prediction models, the area under the receiver operating characteristic curve (AUC) will be used to assess the discriminatory power of the predictive model on a separate sample of subjects. With 10 years incidence rate of ESRD was 3.8%(8), a total 14,307 subjects (544 subjects with ESRD and 13,763 subjects without ESRD) is needed to

ensure a precision of 0.05 for AUC of 0.7 by a 95% confidence interval.

Hence, a total 35,360 male and 35,360 female are needed for the development (training dataset) and validation of risk prediction models stratified by gender. The HA data set that we have obtained for our 5-year evaluation of quality of care and effectiveness of RAMP-DM study(8) has identified 120,857 DM patients under the care of public primary care on or before 1 Jan 2009, so we should be able to obtain sufficient number of subjects.

(iii) **Methods**

Each patient will be followed from 1 July 2006 to 31 December 2016 for the development of the indicator DM complications and mortality.

Definition of indicator DM complications

The incidence of four major DM complications (CHD, stroke, heart failure and ESRD), total CVD and all-cause mortality will be calculated. The incidence is counted from the earliest date of documented diagnosis defined by the relevant ICPC-2 and/ or ICD-9-CM coding recorded in the HA CMS database from 1 July 2006 to 31 December 2016. The relevant ICPC-2 and ICD-9-CM codes of each DM complication and mortality are determined by the academic and HA clinician co-investigators as listed below:-

1. CHD (ischaemic heart disease, myocardial infarction (MI), coronary death or sudden death) is defined by any of ICPC-2 K74 to K76 and ICD-9-CM 410.x, 411.x to 414.x, 798.x

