2. Stoke (fatal and non-fatal stroke) is defined by any of ICPC-2 K89 to K91 or ICD-9-CM 430.x to 438.x.
3. Heart failure is defined by any of ICPC-2 K77 or ICD-9-CM 428.x
4. CVD is defined as the presence of any of CHD, heart failure and stroke ICPC-2 or ICD-9-CM codes listed in 1, 2 and 3 above.
5. ESRD is defined by any of ICD-9-CM 250.3x, 585.x, 586.x, or an eGFR<15mL/min/1.73m².
6. Mortality is identified from the Hong Kong Death Registry.

Risk factors to be Included in the Risk Prediction Models

Risk factors (independent variables) previously found to be associated with DM

complications from the literature (4) and those that are routinely available in primary care are selected to strike a balance between comprehensiveness and feasibility. The potential risk factors that will be explored include those related to patient's socio-demographics, clinical parameters, disease characteristics and treatment modalities. Patient socio-demographics include sex, age and smoking status. Clinical parameters include body mass index (BMI), haemoglobin A1c (HbA1c), systolic and diastolic blood pressure, lipid profile (total cholesterol, HDL-C, LDL-C, triglyceride), estimated glomerular filtration rate (eGFR) and albuminuria. Disease characteristics include the duration of DM and co-morbidity. Treatment modalities include the use of specific anti-hypertensive drugs, insulin, specific oral anti-diabetic drugs and lipid-lowering agents. The operational definitions of the risk factors are shown in appendix A. These factors, except sex, age, duration of DM and co-morbidity, are modifiable, which have implications for practice.

Data collection

In the middle of 2017, anonymous data from 1 January 2006 to 31 December 2016 of all DM patients who satisfy the inclusion criteria and without any exclusion criteria will be extracted by the HA statistics team from the HA clinical management system (CMS) database. We have successful experience in working with the HA in the extraction of similar data from 2009 to 2013 for our extended evaluation on quality of care and effectiveness of RAMP-DM study (7), and we have obtained preliminary agreement from the HA for the data extraction in the present study.

Outcome Measures

1. The incidence of total CVD, all-cause mortality and each of 4 major DM complications over 10 years
2. Factors predictive of total CVD, all-cause mortality and each of 4 major DM complications over 10 years

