Multiple imputation will be used to handle missing data. Multiple imputation aims at increasing the power of the analysis and producing more reliable and applicable models within clinical practice. It also takes subjects with incomplete data into account to avoid unnecessary biases. Each missing value will be imputed five times by the chained equation method, which was equivalent to attain a relative efficiency of 95%. For each of the five imputed datasets, the same analysis will be performed with the five sets of results combined based on Rubin's rules.

2. Misclassification bias from the use of administrative database

This study relies on doctor entries of clinical diagnosis on DM complications and co-morbidity indicated by pre-defined by ICPC-2 and ICD-9-CM codes, which may be subject to misclassification bias. We will cross-check the diagnosis and prescription relation, and compare diagnosis from hospital and primary care records for the same patient in order to assess the data quality.

[Word Count: 3698]

e) Timetable of Work

June – August, 2017:

- i. Recruitment, training of RA
- ii. Meeting and discussion with HA co-investigators and Statistics team to confirm the data extraction schema and operation definitions

September – December, 2017

- i. Extraction of data from HA CMS
- ii. Update literature review

January – March, 2018:

- i. Data cleaning
- ii. Data analysis on the incidence & risk factors of DM complications and mortality

April – December, 2018:

- i. Data analysis to develop 6 prediction models
- ii. Validation of the prediction models

January -May 2019:

- i. Development of 10-year CVD risk prediction nomograms
- ii. Development of 10-year CVD risk prediction charts
- iii. Preparation of manuscripts for publications
- iv. Preparation of final report.

f) Existing Facilities:

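### Eligibility counts attendances from 1 July 2005 but data extraction starts on 1 January 2006, so half of the eligibility window yields no baseline data

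*Combined protocol and SAP*

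**What the plan says.** Four parts of the protocol bear on this point.

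- **Eligibility** (Subjects, Inclusion criteria, item 2): "At least 1 GOPC/FMC attendance on or within 1 year before 1 July 2006". The diabetes code (item 3, "Had a CMS record of the coding of ICPC-2 of T89") and the exclusion for earlier complications ("Patients who had a diagnosis of any DM complications defined by the relevant ICPC-2 or ICD-9-CM") look back from the same date with no lower limit.
- **Extraction** (Methods, Data collection): the request is for "anonymous data from 1 January 2006 to 31 December 2016 of all DM patients who satisfy the inclusion criteria".
- **Baseline** (Methods, opening sentence): "Each patient will be followed from 1 July 2006 to 31 December 2016". Baseline is thus 1 July 2006, and 1 January to 1 July 2006 is the only pre-baseline period in the extract.
- **Predictors and missing data**: "Treatment modalities include the use of specific anti-hypertensive drugs, insulin, specific oral anti-diabetic drugs and lipid-lowering agents" (Risk factors to be Included in the Risk Prediction Models). For definitions, "The operational definitions of the risk factors are shown in appendix A"; that appendix is not in the text available for review. Under Strategies against anticipated problems, item 1, "Multiple imputation will be used to handle missing data". The text does not say whether a patient without a prescription record counts as missing or as not treated.

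**The concern.** The period that makes a patient eligible and the period that supplies baseline predictors should match, or the protocol should explain why they differ. Here extraction begins about halfway through the eligibility year, and no section reconciles the two dates.

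Two consequences follow. First, laboratory values, blood pressure, BMI and prescriptions recorded in July to December 2005 are not requested for anyone. A patient with no later pre-baseline reading then needs imputation, although a real value may exist.

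Second, drug use is unlike a laboratory value. A missing HbA1c is visibly blank, whereas a missing prescription can look the same as no treatment. Imputation fills only what has been flagged as missing. If absence of a record were read as non-use, the coded non-users would include some true users and the treatment log hazard ratios would shrink towards zero. Those log hazard ratios become the weights in the risk equations (Development of risk prediction models).

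The patients concerned attend infrequently, so they may not be a random subset. The planned validation would not show the problem, because the validation third is a random part of the same cohort and carries the same gap.

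**Working it through.** The protocol gives no figure for the overlap of the two windows, so there is none to reproduce. The sample-size figures do not enter this check.

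**Step 1: the date gap (from the protocol alone).**
- Eligibility window: 1 July 2005 to 1 July 2006 = 365 days (366 if both end dates are counted).
- Part before extraction starts: 1 July to 31 December 2005 = 184 days.
- 184/365 = 50.4%; 184/366 = 50.3%.
- Pre-baseline days in the extract: 366 − 184 = 182 (1 January to 1 July 2006, both ends counted).

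If extraction began on 1 July 2005, or criterion 2 began on 1 January 2006, the uncovered part would be 0 days.

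**Step 2: share of eligible patients whose attendances all fall in the gap (assumption needed).** The protocol gives no visit frequency, so only a range can be shown. Two visit patterns bracket it.

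*Irregular visits.* Assume Poisson visits with mean m per year, given at least one in the window. Then

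share = exp(−m × 182/366) × [1 − exp(−m × 184/366)] / [1 − exp(−m)].

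| Mean visits per year (assumed) | Share with no attendance in the extracted pre-baseline period |
|---|---|
| 1 | 38% |
| 2 | 27% |
| 4 | 12% |
| 6 | 4.8% |
| 12 | 0.3% |

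For m = 4: exp(−1.989) × [1 − exp(−2.011)] / [1 − exp(−4)] = 0.137 × 0.866 / 0.982 = 0.121.

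*Regular visits.* If appointments are kept at a fixed interval of six months (182 days) or less, at least one falls in the 182 extracted days, and the share is 0.

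**Step 3: possible dilution of a treatment coefficient (assumption needed).** This applies only if absence of a record is coded as non-use. Assume true drug prevalence p = 0.5 and that a fraction m′ of true users is coded as non-users. Neither value comes from the protocol.

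- Share of coded non-users who are true users: f = p·m′ / (p·m′ + 1 − p).
- Diluted hazard ratio: HR / (1 − f + f·HR).
- m′ = 0.05: f = 0.025/0.525 = 0.048. HR 2.0 becomes 2/1.048 = 1.91; HR 1.5 becomes 1.5/1.024 = 1.47.
- m′ = 0.20: f = 0.10/0.60 = 0.167. HR 2.0 becomes 2/1.167 = 1.71; HR 1.5 becomes 1.5/1.083 = 1.39.

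Step 1 is fact. Steps 2 and 3 only show how the size depends on quantities that the protocol does not state.

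**The case against.** A reader might infer that treated patients will be coded as untreated and that the treatment coefficients will therefore be biased. The documents do not support that. The coding rule is left to Appendix A, which could set drug use to missing when there is no attendance. The imputation plan covers missing risk factors and does not exempt treatment. Some of these patients may also have prescriptions from other Hospital Authority clinics in January to June 2006.

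A reader might also infer that the late start undermines the diabetes and prior-complication criteria. That does not follow either. Those criteria have no lower date limit, and the Hospital Authority statistics team must consult earlier records to apply them. The extraction date may limit only the analysis variables.

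Three further objections have weight.

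- The affected group may be small. Patients on continuing drugs plausibly attend more often than the average eligible patient, and scheduled follow-up at six months or less removes the group altogether. Someone unseen in primary care for six months before baseline may also no longer be on treatment.
- Laboratory, blood pressure and BMI gaps are recognisable as missing and fall under the imputation plan. Their loss costs precision; bias has not been shown.
- The timetable schedules a meeting with the statistics team in June to August 2017 to settle the extraction schema and definitions, before extraction in September to December 2017. The mismatch could be caught there.

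These points limit the consequence but do not close the gap. However Appendix A is written, it cannot use records that were never extracted, and the planned meeting is an opportunity to correct the date, not evidence that it has been corrected. To apply criterion 2, the team must already consult attendances from July to December 2005, which suggests that earlier records can be reached.

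**Conclusion.** The mismatch stands: 184 of 365 days (50%) of the eligibility window yield no baseline predictor data, and nothing in the protocol reconciles the dates. Confidence in this part is high; it rests only on the stated dates, with the extraction date read as limiting the predictor data.

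The consequence ranges from avoidable imputation to dilution of the treatment coefficients. The second needs absent prescription records to be coded as non-use, which the available text neither states nor rules out; confidence that this could occur is moderate. The share of patients affected is unknown and could be close to zero under regular follow-up. The hazard ratios in step 3 are illustrations and should not be quoted as expected bias. No effect on AUC, calibration or risk grouping has been calculated.

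This is a cheap improvement to make before extraction, not a flaw that invalidates the models.

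**What to change.** - **Align the windows.** Under Data collection, move the extraction start from 1 January 2006 to 1 July 2005. If earlier data cannot be obtained, restrict inclusion criterion 2 to attendances from 1 January 2006.
- **State the coding rule.** In Appendix A, set baseline drug use to missing, not to non-use, for any patient with no attendance record in the extracted pre-baseline period. Once the windows match, no eligible patient should be in this position and the rule is a safeguard. If they are left as they are, it is essential.
- **Report the number.** Give the count of patients with no GOPC/FMC attendance from 1 January to 1 July 2006, which replaces the assumed range above with a fact.

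How far back a prescription counts as baseline use is a separate trade-off: a longer look-back captures more users but also counts some who have stopped. It should be stated, but this point does not require a particular choice.

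**Cost.** The preferred change is one date in the data request and a slightly larger extract; the sample-size figures are unaffected. The alternative makes the eligible pool slightly smaller, and the reduced pool should be checked against the required 2 × 35,360 = 70,720 patients.

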3. 10-year risk prediction models for total CVD, all-cause mortality and each of 4 major DM complications
4. Factors that have sufficient power to classify Chinese DM patients in primary care into risk group in terms of total CVD and all-cause mortality.

(iv) **Data processing and analysis**

The cohort will be stratified by gender. Descriptive statistics will be used to calculate the incidence of total CVD, all-cause mortality and each of 4 major DM complications will be analysed annually and cumulatively over 10 years with a 95% confidence interval. The distribution of risk factors will be cross-tabulated by complication or mortality events. The 10 year cumulative incidence of various DM complications and mortalities will be further analysed by Kaplan-Meier method. The Kaplan-Meier survival curve will be used to describe the survivorship of total CVD, all-cause mortality and each of 4 major DM complications in the study cohort over 10 years. Unadjusted associations between the risk factors and odds of events will be assessed by independent t-test for continuous variables or Chi-square test for categorical variables.

The cohort will be randomly split on a 2:1 basis, with the two-third sample used for developing the risk prediction models, and the other one-third sample used for validation of the risk prediction models. The analyses will be carried out separately for men and women.

Development of risk prediction models

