Cox proportional hazard regressions with forward stepwise method will be used to develop the risk prediction models for total CVD, all-cause mortality and each of 4 major DM complications. If the main term of a clinical parameter is selected in the models, the quadratic term of such clinical parameter will be evaluated. Afterwards, the interaction terms between selected predictors and age will be also examined in the risk prediction models. Cox regressions is the most commonly used method in risk prediction models in the Framingham Heart Study (9, 10) and UKPDS (11, 12). It allows us to estimate the risk of disease or death for an individual, given their prognostic variables. A positive hazard ratio means a higher likelihood of event associated with that specific variable. Conversely, a negative hazard ratio means a lower likelihood of the event associated with that specific variable. The key proportional hazards assumption will be assessed by examining plots of the scaled Schoenfeld residuals against time for the covariates. Any non-random pattern indicates a violation of the proportional hazards assumptions in which case transformation of covariates may be considered. For example, all continuous variables were naturally logarithmically transformed to minimize the influence of extreme values and to

improve discrimination and calibration of the models. A parametric approach such as exponential or Weibull distribution for the hazard function can also be carried out. A total of 6 risk prediction models will be established for total CVD, all-cause mortality and each of 4 major DM complications. The log of the hazard ratio of each selected risk factor in the final model will be used as coefficient weights in the prediction model of each relevant outcome. The risk equations for 10 year's follow-up will be established by combining these weights with the survivor function(9). A receiver operating characteristic (ROC) curve of predicted risk against observed events will be used to determine the risk threshold for the predicted outcomes as the risk threshold with the highest sum of sensitivity and specificity of the actual observed events.

Validation of risk prediction models

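### Deaths before a complication have no stated handling; if censored, the Kaplan-Meier and Cox 10-year risks of five of the six outcomes are overstated

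*Combined protocol and SAP*

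**What the plan says.** In *d)(iv) Data processing and analysis* the incidence of each outcome is first described annually and cumulatively. Then: "The 10 year cumulative incidence of various DM complications and mortalities will be further analysed by Kaplan-Meier method". Complications and mortality are treated alike.

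In *Development of risk prediction models* all six outcomes get Cox regression, and the 10-year risk equations "will be established by combining these weights with the survivor function(9"). A ROC curve "will be used to determine the risk threshold for the predicted outcomes".

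*Exclusion criteria* remove "Patients who had a diagnosis of any DM complications defined by the relevant ICPC-2 or ICD-9-CM" codes on or before 1 July 2006. Under *(iii) Methods*, "Each patient will be followed from 1 July 2006 to 31 December 2016".

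In *Definition of indicator DM complications*, "The incidence is counted from the earliest date of documented diagnosis". The CHD definition includes "coronary death or sudden death", and the stroke definition includes fatal stroke. Total CVD takes in both. Heart failure and ESRD list no fatal component. Mortality comes from the Death Registry.

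The text contains no censoring rule, and it names no competing-risk method, cumulative incidence function, cause-specific model or subdistribution model. *Strategies against anticipated problems* covers only missing risk-factor data and misclassification. Appendices A and B are not in the public text; they are described as risk-factor definitions and sample size.

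**The concern.** Censoring a death treats that patient as still able to have the event later, at the same rate as the survivors. One minus Kaplan-Meier, or one minus a Cox survivor function, then estimates risk in a world without other deaths. It exceeds the proportion of patients who will actually have the event. The Cox hazard ratios remain valid as cause-specific hazard ratios; the error lies in the absolute risk.

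Absolute risk is what this study delivers. The nomogram and chart display it, and the chart sorts patients at 10% and 20% CVD risk. The introduction justifies the work by saying that existing models overestimate risk in this population, so a new upward bias works against its purpose.

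The overstatement grows with competing mortality, so it is largest in older patients, and a single recalibration factor would not remove it. There is no upper age limit, and the example nomogram scale runs to 80. Validation may not expose the problem: the calibration plot does not define observed incidence, and a Kaplan-Meier comparator would carry the same bias.

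**Working it through.** **Role of death.** Entry on 1 July 2006 and follow-up to 31 December 2016 give 10.5 years. Nobody is administratively censored before year 10, and the documents name no other exit except death. The handling of death is therefore what separates 1-KM from the simple proportion with the event. Censor deaths and 1-KM is too high; keep them in the risk set to year 10 and the two agree. The plan's text allows either.

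**The plan's own figure.** For ESRD the plan takes a 5-year incidence of 1.9%, "which can be extrapolated to a 10-year incidence of ESRD was 3.8"%: 2 × 1.9% = 3.8%. The development sample follows: 16 × 50 / 0.038 = 21,052.6, rounded up to 21,053. Adding 14,307 for validation gives the stated 35,360. I use 3.8% below only as an example risk level; the documents allow no computable effect on the sample size.

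**Inputs.** Displayed risk R: 3.8% (ESRD), and 10% and 20% (the chart cut-offs). Competing death M is the net 10-year risk of a death not counted as the event. The documents give no value, so M is assumed at 5%, 10%, 20%, 30% and 40%. The last two rows illustrate older subgroups only; nothing in the text supports them for the whole cohort.

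**Formula, constant hazards.** λ = −ln(1−R)/10 and μ = −ln(1−M)/10.

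Actual risk = λ/(λ+μ) × [1 − (1−R)(1−M)].

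- R = 20%, M = 20%: λ = μ, so 0.5 × (1 − 0.64) = 18.0%. Ratio 20/18 = 1.111.
- R = 20%, M = 10%: 0.0223/(0.0223 + 0.0105) = 0.679; 0.679 × 0.28 = 19.0%. Ratio 1.052.
- R = 3.8%, M = 10%: 0.00387/(0.00387 + 0.01054) = 0.269; 0.269 × 0.1342 = 3.61%. Ratio 1.053.

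**Other hazard shapes.** Actual risk = ∫₀¹⁰ h(t) exp[−H(t) − G(t)] dt, where h and H are the event hazard and cumulative event hazard, and G is the cumulative death hazard. Weibull hazards are scaled to the same R and M. Equal shapes for event and death give the constant-hazard result. The last two columns let one hazard rise (shape 1.5 to 2) while the other stays constant.

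| Assumed M | Actual, shown 3.8% | Actual, shown 10% | Actual, shown 20% | Overstatement, constant hazards | Only death hazard rises | Only event hazard rises |
|---|---|---|---|---|---|---|
| 5% | 3.70% | 9.75% | 19.5% | 2.5–2.6% | 1.6–2.0% | 3.0–3.5% |
| 10% | 3.61% | 9.50% | 19.0% | 5.2–5.3% | 3.3–4.2% | 6.3–7.2% |
| 20% | 3.41% | 8.98% | 18.0% | 11.1–11.5% | 7.1–9.0% | 13.7–15.8% |
| 30% | 3.20% | 8.44% | 16.9% | 18.1–18.8% | 11.3–14.6% | 22.6–26.3% |
| 40% | 2.98% | 7.87% | 15.8% | 26.5–27.5% | 16.2–21.1% | 33.5–39.3% |

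**Patients placed in the wrong band.** Solving for the displayed value at which actual risk equals the cut-off:

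- 20% cut-off: 21.0% at M = 10% (20.7–21.4% over all shapes) and 22.2% at M = 20% (21.4–23.1%).
- 10% cut-off: 10.5% (10.3–10.7%) and 11.1% (10.7–11.6%).

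A patient displayed between the cut-off and that limit has an actual risk below the cut-off.

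**Simulation.** One million patients, 10.5 years of follow-up, constant hazards, deaths censored. With R = 20% and M = 20%, the crude proportion is 18.0% and 1-KM is 20.0%. With R = 20% and M = 10%, they are 19.0% and 20.0%. With R = 3.8% and M = 20%, they are 3.4% and 3.8%.

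**The case against.** The strongest reply is that the effect may be small and falls least where decisions are made. The 10% and 20% bands apply only to CVD, and coronary, sudden and stroke deaths are meant to count as CVD events, so fewer deaths compete. The most exposed outcomes, heart failure and ESRD, have no bands, nomogram or chart. Patients are free of complications at baseline, and at 5–10% competing death a displayed 20% is really 19.0–19.5%. All of this stands, and it limits the weight of the point. It does not remove it: other deaths still compete with total CVD, and a cardiovascular death without a code in the clinical system could be missed as an event.

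Second, the plan also reports descriptive incidence. With no other censoring before year 10, a crude proportion equals the Aalen-Johansen estimate, so one correct number may already be planned. Likewise, ROC analysis against observed events naturally counts earlier deaths as non-events. These readings are fair, and a crude comparator in calibration would reveal the bias. Neither corrects the risk equations, and two different 10-year incidences could be reported for one outcome.

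Third, the plan cites the use of Cox regression in the Framingham study and UKPDS. Precedent does not change what the survivor function estimates.

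**Conclusion.** The concern holds. The stated methods, used in the standard way, overstate actual 10-year risk for total CVD, CHD, stroke, heart failure and ESRD. The direction is certain if earlier deaths are censored and any competing death occurs; the plan does not say whether they are censored. The size rests on assumed mortality. Across the hazard shapes tested, the relative overstatement is about 2–3% at 5% competing death, 3–7% at 10% and 7–16% at 20%, with more in older subgroups. Heart failure and ESRD are most exposed and total CVD less so. This should be fixed before analysis, though its practical effect may be small in low-mortality patients.

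**What to change.** - **Event definitions.** State for each outcome which deaths are events, including how coronary or stroke deaths in the Death Registry without a clinical-system code are treated.
- **Incidence (*d)(iv)*).** Keep Kaplan-Meier for all-cause mortality. For the other five outcomes report Aalen-Johansen cumulative incidence, with death not counted as the event as the competing event. Do the same for the CVD risk-group curves in the nomogram and chart section; the log-rank test there remains valid as a cause-specific comparison.
- **Risk equations.** Keep Cox for all-cause mortality. For the other five, take absolute risk from Fine-Gray models or from combined cause-specific Cox models for event and death, and name the choice before analysis. Fine-Gray keeps the nomogram's single total score. Combined cause-specific models need another nomogram layout, though the chart still works. The optional exponential or Weibull approach needs the same treatment of death.
- **Validation.** Base the calibration plot and modified Hosmer-Lemeshow test on Aalen-Johansen observed risk within groups of predicted risk, and use a competing-risk Brier score. For the ROC threshold, AUC, sensitivity and specificity, count patients who die first as not having the event by 10 years. State that D and R² treat death as the fitted model does.

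**Cost.** No new data. Variable selection, quadratic and age-interaction terms, and validation must be run with the competing-risk model for five outcomes in each sex across five imputed datasets. Reported risks will be somewhat lower.
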